6.8 Hospitalization, ICU, Apnea and Ventilation

Duration of hospitalization will be summarized by treatment group. Hospitalization events will be described using Kaplan- Meier method; the number of events (the hospital discharge), number of censored values (subjects who are not discharged from the hospital at the time of early termination), median and quartiles of time to event with 95%CI will be summarized by treatment group.

The duration of hospitalization is defined as the difference between admission and discharge and will be computed in days using the following formula:

- For subjects who were discharged:
(Discharge date/time – admission date/time) / 86400
- For subjects who were still hospitalized or in ICU at the time of early termination, the censoring date will be the date of termination of the trial and the duration of hospitalization will be derived using the following formula
Trial termination date – admission date + 1

Missing time will be defined as follows for the calculation of duration:

- If the admission time is missing then it is estimated as 00:01

- If the discharge time is missing then it is estimated as 16:00

Hospitalization and ICU duration days, as well as apnea episodes and ventilation will be listed by subject.

7 ANALYSIS OF PHARMACOKINETICS

Individual study drug concentrations, actual sampling time and actual sampling times relative to second study drug administration time will be listed by treatment group and subject.

The sampling time relative to the second study drug administration time will be computed in hours as follows:

- $(\text{Start date/time of sampling} - \text{start date/time of second study drug administration}) / 3600$

The sampling time will be negative for blood samples taken on Day 2 pre-dose.

8 IMMUNOGENICITY ANALYSIS

Immunogenicity will be assessed through listing of individual results by subject, as described in section 8.2.

8.1 Available data

8.1.1 Anti-Drug Antibodies ADA

Immunogenicity of ALX-0171 will be monitored in this trial using MSD-based homogeneous bridging ADA assay via a tiered approach. In a first step, samples are evaluated in a screening assay and are scored possibly ADA positive based on the screening cut-point (SCP), allowing a 5% false positivity rate. Positively screened samples are subsequently analyzed in a confirmation assay, which is a drug displacement assay to confirm the specificity of the ADA screening result. All positively confirmed samples are subsequently analyzed in an end-point titration assay to determine the antibody titer. The $\log_{10}(\text{titer})$ will be reported. The titer represents the last dilution factor of the sample's titration series still scoring positive in the ADA assay. Samples scoring negative in the ADA assay are not titrated and the respective $\log_{10}(\text{titer})$ is reported as $<\log_{10}(\text{Minimal required dilution [MRD]})$ with MRD=24, i.e. $\log_{10}(\text{titer}) < 1.38$.

For each subject, immunogenicity results will be classified based on the presence of pre-existing antibodies (pre-Ab) and the presence of treatment-emergent (TE) ADA, as shown in Table 1. Classification will be performed by the Bioanalytical laboratory (Ablynx GLP-Pharma) performing the ADA sample analysis and reporting both $\log_{10}(\text{titer})$ and subject classification.

Table 1: Subject Classification Based on Pre-Ab and TE ADA Status (ADA Assay)

Subject classification
1. pre-Ab NEG – TE ADA NEG
2. pre-Ab NEG – TE ADA POS
3. pre-Ab POS – TE ADA NEG
4. pre-Ab POS – TE ADA POS

5. pre-Ab POS – TE ADA Equivocal
6. TE ADA inconclusive: pre-Ab NEG - post-dose missing
7. TE ADA inconclusive: pre-Ab POS - post-dose missing
8. TE ADA inconclusive: pre-dose missing - post-dose NEG
9. TE ADA inconclusive: pre-dose missing - post-dose POS

NEG: negative; POS: positive

Note: Subject classification 'Inconclusive TE ADA' (that is generally used in case drug tolerance is exceeded) is not included here since drug washout samples are available for ADA testing.

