Body weight	X															X			
Body height	X															X			
Body temperature	X	X			X	X		X	X			X	X		X	X			
General appearance	X	X			X	X		X	X			X	X		X	X			
Lung auscultation ^o	X	X		X	X	X		X	X			X	X		X	X			
Heart rate	X	X		X	X	X		X	X			X	X		X	X			
SpO ₂ ^m	X	X		X	X	X		X	X			X	X		X	X			
Feeding ⁿ	X	X			X	X		X	X			X	X		X				
Respiratory muscle retractions	X	X		X	X	X		X	X			X	X		X				
Respiratory rate	X	X		X	X	X		X	X			X	X		X				
Randomization		X ^b																	
Clinical response information ^h																→			

Period	Visit	Screening ^{a,b}	Study Drug Treatment Period ^c												In-hospital Post-Treatm. Period ^d	FU Visit (Day 14 ± 2) or Withdrawal Visit	EOS ^e (Day 28±2)			
			Hospitalized Dosing																	
			Day 1			Day 2			Day 3											
Time window / Study procedure	-24h to randomization	-3h ^a to dose	Dose	2h (± 0.5h)	5h (±1h)	-2h to dose	Dose	2h (± 0.5h)	5h (±1h)	-2h to dose	Dose	2h (±0.5h)	5h (±1h)	Morning and Evening						
Daytime coughing	X	X		X	X	X		X	X	X		X	X	X ^p	X	X				
Sleep disturbance from nighttime coughing ^q	X	X				X				X				X	X	X				
Parent/caregiver assessment ^r																	→			
Pharmacokinetics						X ^s	←	s	→	←	s									
Clinical laboratory (hematology and clinical biochemistry)	X ^t															X ^u				
Immunogenicity ^v	X ^w															X ^{u,x}				
Concomitant medications																	→			
Adverse events ^y																	→			

h=hour; FU=Follow-up; EOS=End of Study

Timing of assessments: Pre-dose time points relate to the start of study drug administration procedure, post-dose time points relate to the end of the study drug administration procedure. Throughout the study, study personnel should make every reasonable effort to follow the timing in the schedule of assessments for each subject.

- At the time of screening, all screening assessments are to be performed. If Day 1 pre-dose timing occurs within 3 hours after screening, the assessments already done at screening do not need to be repeated; only the remaining Day 1 (pre-dose assessments) will need to be performed.
- At the time of randomization, subjects should be eligible for study participation as defined in the inclusion/exclusion criteria. Therefore, at a minimum, the SpO₂, feeding, respiratory muscle retractions, and respiratory rate should be evaluated on Day 1 before randomization and dosing, unless these assessments were already performed within the last 3 hours before randomization.

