- Study drug administration should take place within 24 hour intervals (±4 hours) relative to the start of the first dose. For subjects requiring 2 serial nebulizations (subjects weighing ≥10 kg in the 9 mg/kg dose group), the timing of study drug administrations should be relative to the start of their first nebulization. Provided that the clinical response criteria have been met, discharge from the hospital can take place per protocol at the Investigator's discretion from dosing on Day 3 onwards after all required assessments of the 5 hours (±1 hour) post-dose time point have been completed. Subjects who started study drug dosing, but were discontinued prematurely from study drug treatment, should be further monitored according to the in-hospital post-treatment period (if applicable) and should attend the FU and EOS visits.
- The in-hospital post-treatment assessments are to be performed for subjects who are not discharged from the hospital after the completion or discontinuation of study drug treatment.
- For subjects who discontinue the study before Day 14, the Withdrawal visit will be conducted on the day of withdrawal as long as there has been no withdrawal of consent, subject is lost to follow-up or death. If the Withdrawal visit assessments are performed within 6 hours after the Day 1, Day 2, Day 3, or in-hospital post-treatment day assessments have been performed, the assessments already done at the prior time point do not need to be repeated and only the additional assessments to be performed on the Withdrawal visit will need to be performed. No EOS visit needs to be performed after the Withdrawal visit. In case subjects are hospitalized beyond the Day 14 FU visit, the additional assessments (in addition to the in-hospital post-treatment period assessments) of the Day 14 FU visit need to be done on Day 14.

- f. RSV infection will be confirmed either according to routine site practice (polymerase chain reaction [PCR], immunofluorescence or diagnostic quick test), or using a Sponsor-provided commercial kit.
- g. Hospitalization information will include occurrence of ICU transfer, apnea episodes, initiation and type of ventilation and hospital/ICU discharge information.
- h. Assessment of Clinical Response will be done with collection of date and time of adequate oral feeding, as well as stable adequate oxygen saturation on room air of $\geq 95\%$ over a period of at least 4 hours to allow for hospital discharge.

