- s. All subjects will undergo PK analysis sampling (3 PK samples per subject), i.e., blood draws on Days 2-3: 1) pre-second dose, 2) between 0.5 hours and 3 hours post-second dose and at least 1 hour apart from the first sampling, and 3) between 3 hours and 6 hours post-second dose (and at least 1 hour apart from the previous sampling). If sufficient serum remains after PK assessment, exploratory biomarker (KL-6) may also be evaluated.
- t. If all hematology and biochemistry blood parameters required for the study are already known from analysis done as a routine assessment upon arrival at the hospital, collection of screening clinical laboratory samples does not need to be repeated for the purpose of this study. However, the samples should be analyzed at the same local laboratory that will be used for the remainder of the study.
- u. No blood sample needs to be taken in case of premature withdrawal from the study for subjects who did not receive any study drug.
- v. For subjects with a body weight below 5 kg and in case the blood volume needed for local clinical laboratory exceeds 2.5 mL, the sample for analysis of immunogenicity should not be collected at screening and on Day 14, but on Day 1 pre-dose and on Day 28, if possible.
- w. If sufficient serum remains after immunogenicity assessment, exploratory biomarker (KL-6) may also be evaluated. In case the blood sample for immunogenicity was not taken at screening, the sample should be collected at the Day 1 pre-dose time point, if possible.
- x. If sufficient serum remains after immunogenicity assessment, exploratory biomarker (KL-6) may also be evaluated. In case the blood sample for immunogenicity was not taken on Day 14, the sample should be collected at the EOS (Day 28) visit, if possible.
- y. An additional serum sample should be collected (if reasonably feasible) in case a serious and/or severe hypersensitivity reaction judged to be related to study drug occurs.

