1.2.3.5. IMMUNOGENICITY

While immunogenicity has been reported in clinical studies with ALX-0171, no correlation with potential immune-related AEs has been established thus far, neither in adults nor in RSV-infected children.

- In adults, pre-existing antibodies (pre-Ab[§]) were found in 7% (ALX-0171-1.1/11) to 18% (ALX-0171-1.3/13) of the subjects.
- In the Phase 1 study ALX0171-1.1/11, no treatment-emergent ADA (TE ADA) responses were detected, whereas in the Phase 1 studies ALX-0171-1.3/13 and ALX-0171-1.2/13, TE ADA were observed in the serum of 13%-33% of the subjects, respectively.
- In Study ALX0171-C104, pre-Ab were found in 45% of the subjects, while TE ADA was detected in 23% of the infants. Pre-Ab detected in those children may reflect maternal antibodies transferred to the infant via the transplacental route during gestation or during breastfeeding. As the assay cannot discriminate pre-Ab from drug induced TE ADA, it is not clear to what extent the TE ADA detected may represent fluctuating levels of pre-Ab. Currently it is not known to what extent pre-Ab can fluctuate within the short study period (14 days). No effect of ADA on PK was observed.

TE ADA is not expected to have an impact on PK or efficacy given the short treatment duration, as TE ADA do not emerge in considerable amounts within the first 7 days after initial drug administration. It is also unlikely that the pre-existing or TE ADA against ALX-0171 would result in a clinically meaningful safety risk (see section [1.3.2](#) below).

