8.1.2 Neutralizing Anti-Drug Antibodies (NAb)

All samples confirmed positive in the ADA assay will be further characterized in the NAb assay. NAb assay results will be reported as values (ratio is optical density (OD) value over negative control (NC)). No titration will be performed.

Subjects will be classified based on their pre-dose status (i.e. baseline visit) and status on treatment as shown in Table 2. Subject classification based on NAb will be performed by the external provider (Eurofins, UK) performing NAb sample analysis and reporting both ratio (for all received samples) and NAb subject classification. Subjects with no positive ADA samples and no missing visits, will not be analyzed in the NAb assay and will be classified as pre-dose NEG – NEG on treatment.

Table 2: Subject Classification Based on Pre-Dose and TE NAb Status (NAb Assay)

Subject classification
1. pre-dose NEG – NEG on treatment
2. pre-dose NEG – POS on treatment
3. pre-dose POS – NEG on treatment
4. pre-dose POS – POS on treatment
5. pre-dose NEG – post-dose missing
6. pre-dose POS – post-dose missing
7. pre-dose missing - NEG on treatment
8. pre-dose missing – POS on treatment

NEG: negative; POS: positive

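### SAP 8.1.1 has no class for a post-dose ADA sample taken too early, so a dosed child withdrawn in the first 7 days can be listed as TE ADA negative

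*SAP*

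**What the plan says.** SAP 8.1.1 sorts each subject into one of nine classes by pre-existing antibody and TE ADA status. The note under Table 1 describes the usual extra class, TE ADA inconclusive, as one "that is generally used in case drug tolerance is exceeded", and says it "is not included here since drug washout samples are available for ADA testing". The inconclusive classes that remain (6 to 9) all concern a missing sample; class 6, for example, reads "TE ADA inconclusive: pre-Ab NEG - post-dose missing".

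The protocol's Schedule of Assessments puts the routine post-dose immunogenicity sample in the column headed "FU Visit (Day 14 ± 2) or Withdrawal Visit". Footnote u gives the only exemption at withdrawal: "No blood sample needs to be taken in case of premature withdrawal from the study for subjects who did not receive any study drug". The Withdrawal visit takes place on the day of withdrawal, and "No EOS visit needs to be performed after the Withdrawal visit".

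On timing, Protocol 1.2.3.5 states that "TE ADA do not emerge in considerable amounts within the first 7 days after initial drug administration". Protocol 1.3.3 repeats the 7-day figure and expects drug to be cleared by about that time.

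For neutralizing antibodies, SAP 8.1.2 says "Subjects will be classified based on their pre-dose status (i.e. baseline visit) and status on treatment". A subject with no ADA-positive sample and no missing visit is put in the negative–negative class without being assayed.

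**The concern.** The decision to do without the drug-tolerance class rests on post-dose samples being washout samples. The schedule allows one group for whom that is not so: children who received drug and are then withdrawn from the study during or shortly after dosing. Their sample exists, so the missing-sample classes do not apply, and no later sample replaces it. A negative result from a time when the protocol itself expects little TE ADA would be listed as absence of a treatment-emergent response.

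The stake is how individual results are read. SAP section 9 drops the immunogenicity summaries, the pre-Ab and ADA tabulation and the correlation analyses. What is left is a listing of titers, NAb ratios and subject classes, and the class is the only interpretation in it.

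**Working it through.** The plan gives no figure to reproduce here. The check compares sampling times with the Table 1 classes.

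**Inputs**
- Day 1 is the day of first dose (SAP 10.2 counts event onset days this way). Dosing is on Days 1 to 3.
- Follow-up visit: Day 14 ± 2. End-of-study visit: Day 28 ± 2.
- Withdrawal visit: on the day of withdrawal. It is not done after death, loss to follow-up or withdrawal of consent (Protocol 3.6.1.6).
- Emergence of TE ADA: not in considerable amounts within 7 days (Protocol 1.2.3.5).
- Cohort 1: 15 randomized (SAP 1), planned as 12 active and 3 placebo.

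**Days after first dose = study day − 1**
- Follow-up: 12 − 1 = 11 to 16 − 1 = 15.
- End of study: 26 − 1 = 25 to 30 − 1 = 29.
- Withdrawal on Days 1 to 7: 0 to 6.
- Withdrawal on Days 8 to 11: 7 to 10.

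**Where each child ends up, given a pre-dose result and a negative post-dose sample if one is taken**

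| Course | Routine post-dose sample, days after first dose | Table 1 class | Washout premise |
|---|---|---|---|
| Stays in study, including children who only stop study drug | 11–15 | 1 or 3 | fits |
| Below 5 kg, sample moved to Day 28 | 25–29 | 1 or 3 | fits |
| Dosed, withdrawn Days 1–7 for safety or non-compliance | 0–6 | 1 or 3 | does not fit |
| Dosed, withdrawn Days 8–11 for the same reasons | 7–10 | 1 or 3 | past the 7-day mark; no washout time given |
| Death, loss to follow-up, consent withdrawn before sampling | none required | 6 or 7 | not needed |
| Never dosed | none | outside Safety Population | not needed |

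Only the third row conflicts with the protocol's own timing. If the pre-dose sample is also missing, class 8 applies and the result is already inconclusive. A child below 5 kg whose sample was to be moved to Day 28 may have no post-dose sample after early withdrawal, which gives class 6 or 7.

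**NAb.** An ADA-negative withdrawal sample is not sent for NAb testing. Whether the child is then classed negative on treatment depends on whether the absent end-of-study visit counts as missing. SAP 8.1.2 does not define this, and the footnote to mock Listing 16.2.8.1 leaves the condition out.

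**Size.** One child is 1/12 = 8.3% of the planned active group, or 1/15 = 6.7% of those randomized.

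**The case against.** The strongest reply is that the gap may be empty. The SAP was written after termination, with cohort 1 fully enrolled and its IDMC meeting held. The note stands under a heading about available data, so it may simply describe the samples in hand. No document reports an early withdrawal. This stands as a limit on consequence. But the SAP does not say that every child reached Day 14, and SAP 5.1 still tabulates early trial discontinuation with reasons.

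A reader might infer that children removed for the most immune-relevant events are the ones misclassified. The documents do not support that. Severe or serious hypersensitivity, acute respiratory distress, ventilation, prohibited medication, code break and failed initiation on Day 2 or 3 lead to stopping study drug, not to leaving the study (Protocol 3.4.2). Those children are still due at Day 14. Severe or serious hypersensitivity judged related also calls for an extra serum sample (Protocol 3.6.8). What remains is withdrawal from the study by the investigator for safety, or for non-compliance (Protocol 3.4.1).

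Two further points soften the harm. Listing 16.2.8.1 shows the date and time of each sample and Listing 16.2.1.6 shows dosing times, so a careful reader can work out that a sample was early. The laboratories assign the classes under a separate Bioanalytical Analysis Plan, which was not available here and may hold a timing rule. Neither changes the fact that the class printed under the SAP's rule would be wrong.

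**Conclusion.** The point holds as a flaw in a stated classification rule: Table 1 cannot separate a negative washout sample from a negative sample taken 0 to 6 days after first dose. Its weight is modest. It affects individual listed classes only, because no incidence or prevalence is tabulated, so the 8.3% for one active child changes no planned output. It rests on the schedule as written, on Day 1 being the first dose, and on the protocol's 7-day statement.

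Three stronger readings are tempting and are not supported.

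- **That drug masks the assay in these children.** Drug was measurable in the serum of most infants in the first-in-infant study (Protocol 1.2.3.3). But neither half-life nor assay drug tolerance is given, only 1.5 mg/kg was given here, and concentrations in that study were below model predictions (Protocol 3.3.2). The timing argument does not need masking.
- **That early antibodies are impossible.** The protocol says they do not appear in considerable amounts within 7 days, which is weaker.
- **That about 23% of early negatives would be false, within 13% to 33%.** The 23% comes from the first-in-infant study, where Protocol 1.2.3.5 says TE ADA could not be told apart from fluctuating pre-existing antibody. The 13% and 33% come from two adult studies, and a third found none. No false-negative percentage can be given.

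**What to change.** In SAP 8.1.1 and 8.1.2, add a class *inconclusive – post-dose sample too early*. Use it when the only post-dose sample is ADA-negative or NAb-negative and was taken within 7 days of first dose, or before a washout time that the sponsor justifies. Let positive results stand. A cut-off at the Day 14 window is not needed: it would also make negatives from Days 8 to 11 inconclusive, which the 7-day argument does not support unless a later washout time is justified.

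State in 8.1.2 whether a withdrawn child's absent end-of-study visit counts as a missing visit, and bring the Listing 16.2.8.1 footnote into line. Add study day relative to first dose to that listing. If all dosed children were sampled at Day 14 or later, saying so in the note would also close the point for this report.

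The cost is one rule and one class passed to the two laboratories, plus one listing column. The downside is that an affected child moves from negative to inconclusive. If no child is affected, nothing changes.

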8.1.2 Neutralizing Anti-Drug Antibodies (NAb)

All samples confirmed positive in the ADA assay will be further characterized in the NAb assay. NAb assay results will be reported as values (ratio is optical density (OD) value over negative control (NC)). No titration will be performed.

Subjects will be classified based on their pre-dose status (i.e. baseline visit) and status on treatment as shown in Table 2. Subject classification based on NAb will be performed by the external provider (Eurofins, UK) performing NAb sample analysis and reporting both ratio (for all received samples) and NAb subject classification. Subjects with no positive ADA samples and no missing visits, will not be analyzed in the NAb assay and will be classified as pre-dose NEG – NEG on treatment.

Table 2: Subject Classification Based on Pre-Dose and TE NAb Status (NAb Assay)

Subject classification
1. pre-dose NEG – NEG on treatment
2. pre-dose NEG – POS on treatment
3. pre-dose POS – NEG on treatment
4. pre-dose POS – POS on treatment
5. pre-dose NEG – post-dose missing
6. pre-dose POS – post-dose missing
7. pre-dose missing - NEG on treatment
8. pre-dose missing – POS on treatment

NEG: negative; POS: positive

8.2 Immunogenicity Listing

Listing of individual results by treatment group, by subject for all immunogenicity parameters (ADA log10(titer) and NAb response ratio as well as ADA and NAb subject classifications) at each time point will be produced. Samples not evaluated in the NAb assay will be indicated as not analyzed (NA).

ADA (log10 titer) measured for specifics SAEs will be described in the listing presenting all SAEs by subject. "N/A" will be reported for SAEs where no ADA analysis was performed.

